In order to evaluate the association between the HPT and PK parameters, HPT parameters will be plotted separately for fixed puffing and *ad libitum* use against the PK parameters with study product indicated using different symbols for each nicotine concentration level.

In order to evaluate the association between the theoretical nicotine exposure and PK parameters, theoretical nicotine exposure will be plotted separately for fixed puffing and *ad libitum* use against the PK parameters with product indicated using different symbols for each nicotine concentration level.

Safety analysis:

The safety population will comprise all enrolled subjects. Adverse events will serve for the primary assessment of safety data. All safety data will be listed however only P4M3 variants-emergent AEs will be summarized by product variant (fixed puffing regimen and *ad libitum* use will be combined at the product variant level) and P4M3 overall. Other safety measurements (vital signs, etc.) will be summarized per fixed puffing regimen/*ad libitum* use and product.

Sample Size:

The sample size is empirically based, as there is no prior information on which to base the sample size and there is no consideration for statistical hypothesis. A sample of 12 subjects is targeted for the analysis of this study to obtain the precision about the mean and variance for the study objectives. Therefore, in order to ensure 12 subjects completing the study, 16 subjects will be randomized.

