LSM	Least-squares means
mg	milligram
mL	Milliliter

Data and information contained in this document are considered to constitute trade secrets and confidential commercial information, and the legal protections provided to such trade secrets and confidential information are hereby claimed under the applicable provisions of US law. No part of this document may be publicly disclosed without the written consent of PMI.

MedDRA	Medical Dictionary for Regulatory Activities
M RTP	Modified risk tobacco product
ms	Millisecond
n	Number of subjects
NCA	Non-compartmental analysis
ng	Nanogram
NHANES III	National Health and Nutrition Survey III
PD	Pharmacodynamic(s)
PK	Pharmacokinetic(s)
PMI	Philip Morris International
PPM	Parts per million
QTcB	Corrected value of the interval between the Q and T waves on the electrocardiogram tracing, using Bazett's formula
QTcF	Corrected value of the interval between the Q and T waves on the electrocardiogram tracing, using Fridericia's formula
RCF	Relative centrifugal force
RRP	Reduced-Risk Product
SAE	Serious adverse event
SAP	Statistical analysis plan
SD	Standard deviation
SHM	Sample handling manual
SMP	Safety management plan
SOP	Standard Operating Procedure
SQ	Sensory questionnaire
T	Time point
T0	Time point of first product use during study day
t _{1/2}	Half-life
t _{max}	Time to maximum concentration
t _{peak}	Time to peak plasma nicotine concentration
UBC	United BioSource Corporation
ULN	Upper limit of the normal range
ULOQ	Upper limit of quantification
USB	Universal serial bus

Data and information contained in this document are considered to constitute trade secrets and confidential commercial information, and the legal protections provided to such trade secrets and confidential information are hereby claimed under the applicable provisions of US law. No part of this document may be publicly disclosed without the written consent of PMI.

VAS	Visual Analogue Scale
WBC	White blood cell (count)
WHO	World Health Organization
µg	Microgram

Explanation of Terms

The following special terms are used in this protocol:

CC	The term 'cigarette' refers to manufactured and commercially available cigarettes and excludes hand-rolled cigarettes, cigars, pipes, bidis, and other nicotine-containing products.

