4 INVESTIGATIONAL PLAN

4.1 Overall Study Design and Plan

This is a single-center, open-label, concentration-ranging study to evaluate the nicotine PK profile and PD effects in healthy White adult experienced users of closed tank/cartridge e-cigarettes using four different variants of P4M3 or their own e-cigarettes.

A Screening Visit, including a demonstration of the P4M3 by the investigational site personnel, will be conducted within 3 weeks (Day -23 to Day -3) prior to Admission (Day -2) (see [Figure 1](#)).

On Day -2, subjects will be admitted to the investigational site at Admission. Subjects should have been fasting for at least 12 hours prior to Admission. After confirmation of subjects' eligibility, subjects will be enrolled in the study and have a debriefing on P4M3 followed by a product test with P4M3-1.7% *ad libitum* for a maximum of 10 minutes. After the product test, subjects not willing and/or not ready to use (e.g., intolerance) P4M3 will be discontinued and may be replaced. Subjects willing to continue will enter their confinement period of 6 days, from Day -2 to Day 5. Following the product test, subjects will be required to abstain from any nicotine/tobacco containing product use for at least 10 hours until the first product use on Day -1.

On Day -1 to Day 4, subjects will use either their own closed tank/cartridge e-cigarette/e-liquid or one P4M3 variant with two different regimens as described in [Figure 1](#):

- a fixed puffing regimen comprising of 12 puffs in total at a rate of one puff every 30 seconds (± 5 seconds) with HPT recording in the morning.
- *ad libitum* use for 60 minutes (± 5 minutes) with HPT recording in the afternoon

The start of product use of subjects' own e-cigarette and P4M3 variant (first puff) for fixed puffing and for the 60 minutes (± 5 minutes) *ad libitum* use will be defined as T0. T0 should be at approximately the same time (± 30 minutes) for fixed puffing in the morning and for *ad libitum* use in the afternoon for subjects' own e-cigarette on Day -1 (Baseline) and for P4M3 variants on Days 1 to 4. T0 for 60 minutes *ad libitum* use should be at least 10 hours after T0 for fixed puffing. There will be a washout of at least 10 hours following each *ad libitum* product use with respect to the subsequent fixed puffing regimen in the next morning to allow adequate background correction of the fixed puffing regimen-related nicotine plasma concentrations.

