7.3.8 Vital Signs

Systolic and diastolic blood pressure, pulse rate, and respiratory rate will be measured at the Screening Visit, on Admission (Day -2), and on every day of confinement (Days -1 through 5, pre-product use and 60 minutes [± 10 minutes] post end of product use and at Discharge), or at early termination. All parameters will be recorded in the supine position after the subject has rested for at least 5 minutes.

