**Table 8. Event Schedule – Fixed Puffing and *Ad Libitum* Product Use with P4M3 Variants (Days 1 to 4)**

Blood sample	Procedures	Additional information
	Optional morning snack	
	Randomization (Day 1 only)	Sequence 1: P4M3-1.7%; P4M3-1.7%LA; P4M3-3%LA; and P4M3-4%LA Sequence 2: P4M3-1.7%LA; P4M3-1.7%; P4M3-3%LA; and P4M3-4%LA
√	Nicotine baseline plasma sampling prior P4M3 variants use	One blood sample will be taken prior to the start of product use (T0): 15 minutes ± 5 minutes (T-1).
√	Clinical laboratory parameters (hematology, urine analysis, clinical chemistry) (Day 2 only)	Fasting state
	Vital signs prior product use	At least 5 minutes in supine position prior to measurement
	VAS for craving prior product use (x1 T0)	
	Washout	Minimum of 10 hours
	Fixed puffing P4M3 variants with HPT	Fixed puffing regimen comprising of 12 puffs in total at a rate of one puff every 30 seconds (± 5 seconds)
√	Plasma samples for nicotine	Post T0, blood will be drawn at the following time points: T1 after 2 minutes ± 30 seconds, T2 after 4 minutes ± 1 minute, T3 after 7 minutes ± 1 minute, T4 after 10 minutes ± 1 minute, T5 after 15 minutes ± 2 minutes, T6 after 30 minutes ± 2 minutes, T7 after 1 hour ± 5 minutes, T8 after 2 hours ± 5 minutes, T9 after 4 hours ± 5 minutes.

VAS Craving assessment	Post T0, VAS assessments will be assessed at the following time points 4 minutes (± 2 minutes) 10 minutes (± 2 minutes) 15 minutes (± 2 minutes) 30 minutes (± 5 minutes) 1 hour (± 10 minutes) 2 hours (± 10 minutes) 4 hours (± 10 minutes)
SQ assessment	Within 60 minutes after completion of product use
Assessment of cough (VAS, three Likert scales and one open question)	Completed by the subject on site within 30 minutes of product use
Vital signs	At least 5 minutes in supine position prior to measurement, to be conducted at 60 minutes ± 10 minutes post end of product use
Device events malfunctions/misuse	As reported post product use
Washout	Minimum 10 hours
Lunch	
Vital signs pre-product use	At least 5 minutes in supine position prior to measurement
VAS for craving prior product use (x1 T0)	
√ Nicotine baseline plasma sampling (x1 T0) prior P4M3 variants ad libitum use	One blood sample will be taken prior to P4M3 variants ad libitum use (T0): 15 minutes ± 5 minutes (T-1)
Ad libitum use P4M3 variants with HPT	Ad libitum use for 60 minutes (± 5 minutes) with HPT recording

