12.1.1 Definitions for Statistical Data Analysis

Unless otherwise stated, for the purposes of statistical analyses, baseline is defined as the last available time point prior to T0 on Day -1.

Nicotine exposure parameters will be derived from plasma nicotine versus time data by NCA using Phoenix WinNonlin, Version 7.0 or higher. C_{max}, AUCs, and related PK parameters, as appropriate, will also be calculated. To minimize the potential bias in the nicotine plasma PK parameters for the fixed puffing regimens, background-concentration correction will be applied to the concentration data and derived PK parameters to adjust for carry-over effects. For nicotine exposure parameters, baseline (C₀) will be defined as the concentration immediately prior to T0 for each session. The baseline correction will be implemented by calculating the nicotine exposure parameters using adjusted concentration values as described below:

The nicotine terminal elimination rate constant λ_z (and $t_{1/2z}$) will be estimated from the Day 5 PK samples (or early termination samples, if available) using a linear regression on the log concentration the pre-T0 time points. The regression analysis should contain data from at least 3 different time points in the terminal phase (including the last quantifiable concentration but excluding the concentration at t_{max}), consistent with the assessment of a straight line on the log-transformed scale. The nicotine plasma background-corrected PK parameters will be derived by performing the NCA on the corrected concentrations.

For the purposes of background-correction of the plasma concentrations post-baseline the following formula will be applied: $cC_t = C_t - C_0 * e^{-\lambda_z t}$. Where, C_t is the corrected concentration at each time point, C_0 is the pre-use baseline concentration, λ_z is the Day 5 (or early termination, if available) terminal elimination rate constant and t is the actual time.

If plasma concentrations cannot be background-corrected in a sufficient number of subjects e.g., in the event that the λ_z (or $t_{1/2z}$) cannot be estimated, modelling approaches may be applied including conventional compartmental analyses. The total (untransformed) PK parameters will be reported and used for statistical analyses instead in case both correction methods are unsuccessful. If warranted, nonlinear mixed-effect modeling using nicotine pooled data across studies may also be used.

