12.6.3 Safety Endpoints

In general, all safety data will be listed and tabulated using the approach described in [Section 12.1.2](#). Safety variables collected during exposure periods will also be reported by product exposure.

AE data will serve as the primary assessment of safety. Other safety variables monitored in this study include: respiratory symptoms (cough assessment VAS and Likert scales); vital signs (systolic and diastolic blood pressure, pulse rate, respiratory rate); spirometry; ECG data; clinical chemistry, hematology, and urine analysis safety panel; physical examination.

Data and information contained in this document are considered to constitute trade secrets and confidential commercial information, and the legal protections provided to such trade secrets and confidential information are hereby claimed under the applicable provisions of US law. No part of this document may be publicly disclosed without the written consent of PMI.

All AEs will be summarized by nicotine concentration (fixed puffing and *ad libitum* use combined) and overall. The number and percentage of subjects with AEs, SAEs, and device events will be tabulated by system organ class and preferred term. Summaries will also be presented for AEs leading to discontinuation, AEs leading to death, AEs by relatedness to product exposure (with and without laboratory related AEs), AEs by severity, and laboratory AEs. Tabulations will be performed for both the number of subjects experiencing an event and the number of events. Due to the laboratory schedule in this study, any lab related AEs will be assigned to P4M3 4% nicotine concentration.

Summary tables showing actual values and change from baseline of clinical findings will be provided for spirometry, ECGs, vital signs, and laboratory parameter. Descriptive statistics will be summarized by fixed puffing/*ad libitum* use and nicotine concentration and change from baseline will be presented for laboratory parameters, ECG, respiratory symptoms, and vital signs. Shift tables will be provided for laboratory and safety ECG data.

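### Vital-sign change for every P4M3 session is measured from a Day -1 value, although each session has its own pre-use reading, so change scores by product mix acute effect with drift over confinement

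*Protocol*

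**What the plan says.** Section 12.1.1 gives a general baseline that holds wherever nothing else is stated: "baseline is defined as the last available time point prior to T0 on Day -1". Section 12.6.3 plans actual values and change from baseline for vital signs, broken down by regimen and nicotine concentration: "change from baseline will be presented for laboratory parameters, ECG, respiratory symptoms, and vital signs". The synopsis has the same breakdown: "Other safety measurements (vital signs, etc.) will be summarized per fixed puffing regimen" and by product. Neither place gives vital signs a baseline of their own.

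The measurement schedule is paired. Section 7.3.8 requires vital signs "pre-product use and 60 minutes [± 10 minutes] post end of product use" on the days of product use. Table 8 lists one reading before fixed puffing ("Vital signs prior product use") and another before ad libitum use ("Vital signs pre-product use") on Days 1 to 4. Table 7 does the same for Day -1.

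The meaning of T0 is not uniform. The abbreviation list defines it as "Time point of first product use during study day", which is the morning session. Section 4.1 and Section 6.3.2 give each session its own T0; Section 4.1, for instance, says that the ad libitum T0 "use should be at least 10 hours after T0 for fixed puffing".

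**The concern.** The protocol uses a session-specific baseline where it wants one. In Section 12.1.1 the nicotine baseline is the concentration just before T0 of each session, and the synopsis adjusts VAS craving for the value before product use. Vital signs get no such wording, so the Day -1 default governs them.

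A pre-use and a 60-minute post-use reading around each session suit the question of what a product does acutely to blood pressure, pulse and respiratory rate. The planned change score does not use that pairing for any P4M3 session. It compares a post-use reading with a value from an earlier day, so any movement in resting values over confinement enters the figure shown for the product. Because concentration rises with study day in both sequences, a downward drift could hide an acute rise at the highest concentration, and an upward drift could produce an apparent one.

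**Working it through.** No figure in the plan bears directly on this point. The sample size (12 / (1 - 0.25) = 16, as stated) does not enter. The check is a count of readings, the elapsed times, and a short decomposition.

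**Readings.** 5 days (Day -1 and Days 1 to 4) x 2 sessions = 10 pre-use readings per subject. If T0 on Day -1 means the first use of the day, 1 reading is the baseline and 9 are not. If each session has its own T0, 2 readings are baselines and 8 are not. In both cases none of the 8 pre-use readings before P4M3 sessions is a baseline.

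**Elapsed time from baseline to post-use reading.** Inputs: fixed puffing lasts 12 x 30 s = 6 min = 0.1 h; ad libitum use lasts 1 h; the post-use reading is 1 h after end of use; the ad libitum T0 is at least 10 h after the fixed-puffing T0. The pre-use reading is placed at T0 for simplicity. Let i be the number of days after Day -1 (there is no Day 0, so Day 1 has i = 1 and Day 4 has i = 4).

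- Fixed puffing: 24i + 0.1 + 1
- Ad libitum, Day -1 pre-ad libitum baseline: 24i + 1 + 1
- Ad libitum, Day -1 morning baseline: at least 24i + 10 + 1 + 1

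| Day | Fixed puffing (h) | Ad libitum, afternoon baseline (h) | Ad libitum, morning baseline (h, at least) |
|---|---|---|---|
| -1 | 1.1 | 2 | 12 |
| 1 | 25.1 | 26 | 36 |
| 2 | 49.1 | 50 | 60 |
| 3 | 73.1 | 74 | 84 |
| 4 | 97.1 | 98 | 108 |

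With the same session's pre-use reading the interval is 1.1 h (fixed) or 2 h (ad libitum) on every day.

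**Decomposition.** Let a be the acute effect, g a linear drift per day, and s a morning-to-afternoon shift that is present only when an ad libitum reading is set against a morning baseline.

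- Change from Day -1 = a + g x i + s
- Change from the same session's pre-use reading = a

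The documents give no value for a, g or s. The following are assumptions: a = +5 units, g from -1 to +1 unit per day, s from 0 to +5 units. On Day 4:

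- Fixed puffing, or ad libitum with the afternoon baseline: 5 - 4 = 1 to 5 + 4 = 9
- Ad libitum with the morning baseline: 5 - 4 + 0 = 1 to 5 + 4 + 5 = 14
- Same-session baseline: 5 throughout

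**Variant against own e-cigarette within one regimen.** (a_variant + g x i + s) - (a_own + s) = a_variant - a_own + g x i. The shift s cancels and the drift does not. What remains is 3g for 3%LA and 4g for 4%LA, or up to 3 and 4 units either way under the assumed range. The two 1.7% variants swap Days 1 and 2, so with equal numbers per sequence (assumed) each carries (1 + 2) / 2 x g = 1.5g against own product, and the drift cancels between those two.

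**The case against.** The opposing case has four parts.

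First, a reader might infer that all ad libitum changes are measured from a morning value and so carry a time-of-day effect that distorts product comparisons. The documents do not support that. The morning reading rests on the abbreviation-list entry for T0. Sections 4.1 and 6.3.2 give each session its own T0, and Section 12.1.2 keeps the regimens apart in all summaries except AEs. On that reading the ad libitum baseline is the Day -1 pre-ad libitum value. Even on the morning reading, clock times match within 30 minutes across days, so the shift is common to own product and variants and cancels within a regimen. It would affect only absolute ad libitum changes and comparisons between regimens. This objection stands. What is left is an ambiguity to settle.

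Second, the pre-use readings are not lost. Section 12.6.3 tabulates actual values and lists all safety data. If the tables are by time point and data are complete, the post-use mean minus the pre-use mean is the mean within-session change. That stands as mitigation, but the spread of individual pre-to-post changes cannot be recovered from two separate sets of means and SDs.

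Third, the stated objective in Section 3.2 is to monitor safety and tolerability, and Day -1 is the named baseline day. Change from Day -1 is a legitimate measure of cumulative change. Section 4.2 also accepts incomplete nicotine washout, so later pre-use readings are not nicotine-free. This rules out replacing the Day -1 baseline, but not adding a second summary.

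Fourth, the SAP may set baselines for individual variables. That is so, but here the protocol states a default that covers vital signs, and it makes its exceptions elsewhere.

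**Conclusion.** The point holds for drift over days. As written, every P4M3 vital-sign change score spans roughly one to four days where a pre-use reading one to two hours earlier is available. Drift is fully confounded with product for own e-cigarette, 3%LA and 4%LA. Its size is unknown: each unit of linear drift per day adds 3 units to the 3%LA contrast with own product and 4 units to the 4%LA contrast.

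The conclusion rests on the Section 12.1.1 default applying to vital signs. It does not depend on how T0 is read or on the illustrative values. The same-session change removes drift that shifts both readings of a session equally. It does not remove residual nicotine in the pre-use reading or any change over days in the acute response itself.

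The documents do not support claiming a time-of-day bias between products, or calling change from Day -1 a wrong analysis. The consequence is moderate: the endpoint is secondary and descriptive, no hypothesis is tested, and AEs are the primary safety assessment.

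**What to change.** In Section 12.6.3:

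- Add the change from the same session's pre-use reading to the 60-minute post-use reading, by product and regimen, as the summary of acute vital-sign effect.
- Keep change from Day -1 and label it as the summary of cumulative change over confinement.
- State that for ad libitum use the Day -1 baseline is the pre-ad libitum reading, and bring the abbreviation-list entry for T0 into line with Sections 4.1 and 6.3.2.

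The cost is a sentence or two of text and one additional descriptive table. All readings are already scheduled, so no procedure changes.

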12.7 Exploratory Analyses

There are no planned exploratory analyses.

12.8 Interim Analysis

Quality controlled data of plasma nicotine concentrations will be analyzed. The analysis on the quality controlled data will be performed prior to database lock and the outcome of the analysis will be received and reviewed by the Sponsor. Following this analysis, all data changes and changes to the statistical analysis will be documented in the study report including an assessment of the impact of the change and the status of the data at the time of the change. Alternative modeling approaches will be defined in the statistical analysis plan prior to performing the analysis.

13.2 Subject Confidentiality

All information obtained during the conduct of the study with respect to the subjects' state of health will be regarded as confidential. A statement to this effect will be written in the information provided to the subject. An agreement to disclose any such information will be obtained from the subject in writing and signed by the subject, in compliance with all local and national data protection and privacy legislation.

The confidentiality of data for subjects participating in this study will be maintained. Subjects will be identifiable by the Sponsor (or Sponsor's authorized representative) on CRFs and other documents by their subject number/code, sex and date of birth, but **not** by name, initial, or any other details relating to an identifiable person (e.g., address, social security number, medical chart number, etc.) The assignment of a subject number/code for subject identification will be based on the appropriate data protection rules.

Any documents that allow full identification of the subject (e.g., the subject's signed study information sheet and ICF) must be maintained in confidence by the Investigator. If any document relating to this study shows a subject's name or any other details relating to an identifiable person (e.g., address, social security number, medical chart number, etc.), the name or other identifiable details must be obscured before a copy of that document is supplied to the Sponsor or the Sponsor's authorized representative.

